15.2.2 Other Secondary Efficacy Endpoint Analyses

Other secondary efficacy endpoints will be summarized descriptively according to the type of outcome. ACR50 at Week 12 will be presented by subgroups as defined in Section 10.2.6 for ITT analysis set, but there will be no breakdown by subgroup for the remaining efficacy endpoints. All analyses will be carried out on both the ITT and the PP analysis sets.

15.2.2.1 ACR20 at Weeks 2, 4, 8, 24, and 52

These endpoints will be analyzed as per the key secondary endpoint (see Section 15.2.1).

Additionally, time to achieve ACR20 response will be will be measured from Trial Day 1. The subjects who did not achieve ACR20 before or at Week 52 will be censored at the date of their last ACR assessment prior to or at Week 52. Subjects who did not have any post-baseline ACR assessment will be censored at time = 1 day.

Results will be summarized by means of Kaplan-Meier curves together with a summary of associated statistics (median, confidence interval) and the number of subjects under risk on the ITT analysis set.

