The first 2 doses of IMP will be administered on site by the Investigator or other qualified personnel and the patient will be educated on the correct process. The third dose of IMP will be administered on-site by the patient. Patients will be monitored for 1 hour following the first 3 IMP administrations. If the Investigator judges it appropriate after proper training, the patient (or a caregiver) may continue to self-inject/inject the treatment for the remaining doses. Injection site pain will be assessed after doses 3 to 5. If a patient self-administers, the injection should not be given in the arm. The remaining doses of IMP will be dispensed, and written instructions on proper dosage, administration, storage, and recording will be provided to the patient/caregiver. Administrations performed at home will be recorded in a diary with the accurate dosing information (dosing date and time).

The 52-week double-blind period will allow for the collection of long-term comparative safety, immunogenicity, and efficacy data for MSB11022-**CCI** versus Humira®.

Patients who achieve less than 20% improvement in both swollen and tender joint counts at Week 24 (non-responders) will be discontinued from the IMP. These patients will remain in the trial safety analysis set and participate in the safety and immunogenicity assessments. After Week 24, patients with less than 20% improvement in both swollen and tender joint counts at any scheduled visit up to Week 52 will also be discontinued. Patients may continue at Investigator discretion from Week 24 to Week 52 as long as they maintain more than 20% improvement in both swollen and tender joint counts.

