The first 2 doses of IMP will be administered on site by the Investigator or other qualified personnel and the patient will be educated on the correct process. The third dose of IMP will be administered on-site by the patient. Patients will be monitored for 1 hour following the first 3 IMP administrations. If the Investigator judges it appropriate after proper training, the patient (or a caregiver) may continue to self-inject/inject the treatment for the remaining doses. Injection site pain will be assessed after doses 3 to 5. If a patient self-administers, the injection should not be given in the arm. The remaining doses of IMP will be dispensed, and written instructions on proper dosage, administration, storage, and recording will be provided to the patient/caregiver. Administrations performed at home will be recorded in a diary with the accurate dosing information (dosing date and time). In the case that there is a delay in the administration of IMP at home, there will be no delay to scheduled visits. During weeks with scheduled trial site visits, the IMP will be administered at the site.

The 48-week double-blind treatment period will allow for the collection of long-term comparative safety, immunogenicity, and efficacy data for MSB11022-**CCI** versus Humira®.

Patients who achieve less than 20% improvement in both swollen and tender joint counts at Week 24 (non-responders) will be discontinued from the IMP. These patients will remain in the trial safety analysis set and participate in the safety and immunogenicity assessments. For the management of these patients, see Section 5.4.1.

After Week 24, patients with less than 20% improvement in both swollen and tender joint counts at any scheduled visit up to Week 52 will also be discontinued. Patients may continue at Investigator discretion from Week 24 to Week 52 as long as they maintain more than 20% improvement in both swollen and tender joint counts.

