Patients who discontinue from the study medication but remain in the trial and continue for the safety/immunogenicity visits before the Week 52 visit will immediately complete an Early Termination visit and return for a Safety/Follow-up visit 4 weeks after the last dose of IMP. During this 4-week Safety Follow-up period, no excluded treatment for RA (as defined in this protocol) should be administered. Patients will return for an additional safety evaluation 4 months after the last dose of IMP. Treatment for RA from the 4-week Safety Follow-up visit to the 4-month Safety Evaluation visit will be at the discretion of the Investigator following institutional standard of care. The 4-week and 4-month Safety Follow-up visits will not be duplicated if either of these visits falls within 2 weeks of an otherwise scheduled visit. If the 4-week and 4-month Safety Follow-up

since last IMP are completed within the 52 week visit schedule, these will not be repeated thereafter.

All patients will have PK samples taken pre-first dose, and then prior to dosing on Weeks 2, 4, 12, 24, 36, and 52. In addition, a subset of 60 patients (30 per arm) will have additional samples to support the population PK analysis taken on Days 2 (24 h post first dose), 4, and 9, and Days 2 (24 h post Week 24 dose), 4, 9, and 14 (Week 26 pre-dose) after the Week 24 dose (see [Table 2](#)).

An IDMC will review the safety data from this trial on an ongoing basis.

Visit schedules for safety, immunogenicity, and efficacy assessments are detailed in the Schedule of Assessments in [Table 1](#).

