#### **5.4.2 Withdrawal from the Trial**

Patients may withdraw from the trial at any time without giving a reason. Withdrawal of consent will be considered withdrawal from the trial. The Investigator should make every attempt to clarify the level of withdrawal: eg, whether or not banked samples can still be retained and evaluated, if the patient can still be contacted by phone for checking his/her status (eg, alive or not), or to return for safety visits. In case of withdrawal from the trial for reasons other than consent withdrawal, the assessments scheduled for the early termination visit should be performed immediately and return for a Safety/Follow-up visit 4 weeks after the last dose of IMP. Patients will return for an additional safety visit 4 months after the last dose of IMP. In any case, the appropriate CRF section must be completed. Patients will be asked to confirm that any samples collected but not yet analyzed can be utilized.

Patients withdrawn from IMP will continue the safety and immunogenicity follow-up until the end of the trial (also see Section 5.4.1 for specific details). These patients will be managed based on the Investigator's clinical judgment and per local guidelines, and any new medication prescribed in such a period will be recorded. In any case, the appropriate case report form (CRF) section must be completed.

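### The Kaplan-Meier curve of time to ACR20 censors never-responders near Week 24 when they are removed for joint-count failure, so its Week 52 step overstates cumulative response on IMP

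*SAP*

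**What the plan says.** SAP 15.2.2.1 adds a time-to-response analysis to the visit-wise ACR20 proportions. Time runs from Trial Day 1, on the ITT set. The SAP states: "Results will be summarized by means of Kaplan-Meier curves together with a summary of associated statistics", and lists the median, its confidence interval and the number at risk. Subjects with no ACR20 by Week 52 "will be censored at the date of their last ACR assessment prior to or at Week 52". ACR20 is planned at Weeks 2, 4, 8, 12, 24 and 52 (SAP 6), so Week 52 is the only planned time point after Week 24.

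The removal rule is in the Protocol Synopsis (Methodology) and in Protocol 5.2: "Patients who achieve less than 20% improvement in both swollen and tender joint counts at Week 24 (non-responders) will be discontinued from the IMP". Protocol 5.2 extends it: "After Week 24, patients with less than 20% improvement in both swollen and tender joint counts at any scheduled visit up to Week 52" are also stopped. On what follows, Protocol 5.2 says: "These patients will remain in the trial safety analysis set and participate in the safety and immunogenicity assessments", and Protocol 5.4.2 says: "Patients withdrawn from IMP will continue the safety and immunogenicity follow-up until the end of the trial". Subjects who stop "will immediately complete an Early Termination visit and return for a Safety/Follow-up visit 4 weeks after the last dose of IMP", with one more visit 4 months after the last dose.

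SAP 15.2.1 defines ACR20 as at least 20% improvement in both the tender and the swollen joint count, plus three of five other measures. Non-responder imputation (SAP 11.4.1) is written for ACR20 at Week 12. No sensitivity or competing-event analysis is given for the time-to-ACR20 curve.

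**The concern.** Kaplan-Meier treats a censored subject as having the same later chance of response as those still at risk. Here the protocol stops subjects for failing a component of the event being timed. A never-responder removed at Week 24 leaves the risk set at about that date. The estimate for Week 52 then comes from never-responders who were allowed to stay on treatment and is applied to those who were not. The reader sees an ITT curve of cumulative response whose last step is partly an extrapolation from a favourably selected group. In a comparison with the reference product, the late curves could look alike even if one arm lost more subjects to joint-count failure.

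**Working it through.** **The plan's own figure.** There is none to reproduce. The documents give no response rate, median or event count for time to ACR20, and no rate of removal for joint-count failure. The only design input used below is 130 per arm (SAP 7.1).

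**When a removed subject is censored.**
1. The Early Termination visit is immediate, so for a Week 24 failure it falls at about Week 24.
2. The 4-month visit comes 4 × 30.4375 / 7 = 17.4 weeks after the last dose (month length from SAP 11.8). With a last dose at Week 22 or 24, that is about Week 39 to 41.
3. SAP 8 ends the data for early terminators at the theoretical Week 52 or the 4-month visit, whichever comes first. For a Week 24 failure the 4-month visit comes first, so no Week 52 ACR assessment would enter the final analysis.
4. The last ACR assessment is therefore at Week 24 or Early Termination, or at the 4-week follow-up if ACR measures are taken there.

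**Formulas.** Let p be the share without ACR20 by Week 24, f the share of these removed, q the first-response rate by Week 52 in those who stay, and q′ the rate in those removed.
- SAP rule: 1 − KM at Week 52 = 1 − p(1 − q)
- Cumulative response with removed subjects followed: 1 − p[1 − (1 − f)q − f·q′]
- Excess = p·f·(q − q′)

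Setting q′ = 0 gives response on IMP. The values of p, f and q are assumptions: p 15–35%, f 40–80%, q 30–50%.

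| p, f, q | SAP rule | Response on IMP (q′ = 0) | Excess, q′ = 0 | Excess, q′ = q/2 | Excess, q′ = q |
|---|---|---|---|---|---|
| 15%, 40%, 30% | 89.5% | 87.7% | 1.8 | 0.9 | 0 |
| 25%, 60%, 50% | 87.5% | 80.0% | 7.5 | 3.75 | 0 |
| 35%, 80%, 50% | 82.5% | 68.5% | 14.0 | 7.0 | 0 |

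The first and last rows are the ends of the range.

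**The middle row in subjects.** Of 130 in an arm, 130 × 0.25 = 32.5 have not responded by Week 24; 32.5 × 0.60 = 19.5 are removed and 13 stay. The stayers yield 13 × 0.50 = 6.5 late responders. Kaplan-Meier credits 32.5 × 0.50 = 16.25. The difference, 9.75, is 7.5% of 130.

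**Simulation check.** Take p = 30%, f = 50%, q = 30%, q′ = 0. The formulas give 79.0% under the SAP rule and 74.5% on IMP. A simulated cohort of 200,000 gives 79.2% and 74.6%. Keeping removed subjects in the risk set to Week 52 also gives 74.6%. The Week 24 value is 70.0% under either rule. The median is Week 12 under either rule, assuming that responders by Week 24 first respond at Weeks 2, 4, 8, 12 and 24 in proportions 20, 20, 25, 20 and 15%.

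**Between arms.** With p = 25% and q = 50% in both arms, but f = 40% in one and 80% in the other, both curves show 87.5%. Response on IMP is 1 − 0.25(1 − 0.6 × 0.5) = 82.5% and 1 − 0.25(1 − 0.2 × 0.5) = 77.5%.

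**The case against.** The strongest reply is that little depends on this number. Time to ACR20 is in no endpoint list. It is descriptive, and SAP 11.2 treats everything beyond the primary endpoint as supportive. The planned summary is the median and number at risk, not a Week 52 percentage, and Week 52 ACR20 is reported separately as a proportion. This limits the importance of the point. It does not repair the curve, which is a planned output drawn to Week 52. If the Week 12 imputation is read as carrying over to other visits through the cross-reference to SAP 15.2.1, it still governs proportions, not censoring.

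The end of ACR follow-up is inferred. No sentence says that efficacy assessments stop, and the late efficacy marks in Protocol Table 1 cannot be placed with confidence in the text available. The inference rests on what is named as continuing and on the cut-off in SAP 8. If removed subjects did contribute Week 52 ACR data, the bias would disappear and the fix would cost almost nothing.

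A reader might infer several stronger things that the documents do not support:
- *That the plan hides an arm difference.* SAP 12.1 tabulates treatment discontinuation by reason and arm. Week 24 ACR20 (15.2.2.1) and joint counts by visit (15.2.2.3) are also shown by arm. These give a partial check, and the 40% against 80% case is constructed.
- *That the late curve holds only subjects with improved joint counts.* Under the wording of Protocol 5.2, a subject failing one count may stay. Footnote a to Table 1 reads as removal for failing either count.
- *That removed subjects are observed non-responders.* After the 4-week follow-up they may receive RA treatment at the Investigator's discretion and could respond. Zero response is right only for response on IMP.
- *That earlier drop-out for lack of effect adds to the bias.* Protocol 5.4.1 lists no lack-of-effect criterion, and the joint-count rule starts at Week 24.

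**Conclusion.** The point holds for the part of the curve after Week 24, which is in effect the Week 52 step. Censoring there is triggered by failing a component of ACR20, so independent censoring is not tenable, and cumulative response (1 − KM) is too high as a measure of response on IMP. If the plot shows subjects not yet responding, it is too low. Only subjects who never reached ACR20 before removal are affected. The curve to Week 24 is not changed by this rule, nor is the median if half respond by then.

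The size rests wholly on assumed rates: about 2 to 14 points if removed subjects never respond, about half that if they respond at half the rate of those who stay, and zero if they respond at the same rate. The comparison between arms is distorted only if stopping rates differ. The change is worth making because it is small and the curve is labelled ITT, but no primary or key secondary result depends on it.

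**What to change.** In SAP 15.2.2.1, add one sentence: subjects removed under the joint-count rule before a first ACR20 response stay in the risk set as not responding and are censored at Week 52. Alternatively, report cumulative incidence with IMP discontinuation before response as a competing event. Label the estimate as response on IMP, and keep the planned curve as a sensitivity analysis.

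Do not extend the first option to every withdrawal as if non-response had been observed; stopping for an adverse event, pregnancy or loss to follow-up is a different matter. SAP 11.4.1 already offers a precedent, since it counts subjects who discontinue before Week 12 as non-responders.

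The wordings of the removal rule in Table 1 footnote a and in the Synopsis and Protocol 5.2 must be reconciled, because they determine who is censored. Joint-count removal should be identifiable as its own reason for stopping; it is not in the list in Protocol 5.4.1.

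The cost is a sentence, a changed censoring date and a slightly less favourable late response figure. No new assessments are needed.

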15.2.2.2 ACR50 and ACR70

ACR50 and ACR70 are defined as an improvement of at least 50% and 70%, respectively, in the number of tender joints and swollen joints, and at least 50% and 70% improvement, respectively, in three out of the remaining five ACR core-set measures (patient pain, Patient's and Physician's Global Assessment of Disease Activity, HAQ-DI and CRP).

These endpoints will be analyzed at Weeks 2, 4, 8, 12, 24, and 52 as per the key secondary endpoint (see Section 15.2.1).

15.2.2.3 ACR Component Variables

Summary statistics will be presented for the actual values for the ACR component variables (tender joint count (TJC), swollen joint count (SJC), Patient's and Physician's Global Assessment of Disease Activity, Patient's Assessment of Arthritis Pain – divided by 10, Patient's Assessment of Physical Function as measured by the HAQ-DI and CRP) and change from baseline values, by visit and treatment arm.

Line graphs will also be provided to display the change from baseline over time for the ACR component variables, by treatment arm.

15.2.2.4 DAS28-ESR

The Disease Activity Score calculated on 28 joints (DAS28-ESR) is a composite score derived from four measures. Components of DAS28-ESR are:

- Number of tender joints (out of the 28)
- Number of swollen joints (out of the 28)
- Erythrocyte sedimentation rate (ESR)
- Patient's Global Assessment of Disease Activity.

For DAS28-ESR, the 28 joints to be examined and assessed as tender or not tender for TJC and to be examined and assessed as swollen or not swollen for SJC include 14 joints on each side of the subject's body: 2 shoulders, 2 elbows, 2 wrists, 10 metacarpophalangeal joints, 2 interphalangeal joints of the thumb, 8 proximal interphalangeal joints, and 2 knees.

DAS28 will be derived using the following formula:

$$DAS28 = 0.56*\sqrt{(TJC28)} + 0.28*\sqrt{(SJC28)} + 0.014*GH + 0.70*ln(ESR)$$

where:

- TJC28 = 28 joint count for tenderness
- SJC28 = 28 joint count for swelling
- ln(ESR) = natural logarithm of ESR

• GH = the general health component of the DAS (i.e., Patient's Global Assessment of Disease Activity, assessed using a scale of 1 to 100 where 100 is maximal activity; For analyses, GH will be divided by ten and converted to a 0.5 scale, i.e. 0, 0.5, 1, 1.5 etc. where [0-0.25] = 0, [0.25-0-75] = 0.5, [0.76-1.25] = 1, etc.).

A DAS28-ESR of > 5.1 implies active disease, < 3.2 low disease activity, and < 2.6 remission. A change of ≥ 1.2 (twice the measurement error) is defined as a significant change of the disease activity state.

The proportion of subjects with DAS28 low disease activity and remission at Weeks 2, 4, 8, 12, 24 and 52 will be reported along with Exact 95% CIs calculated with the Clopper-Pearson method.

Summary statistics will be presented for the actual DAS28-ESR values and change from baseline, by visit and treatment arm. Similarly for the DAS28-ESR component variables.

Line graphs will also be provided to display the change from baseline over time for DAS28-ESR and its component variables, by treatment arm.

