**7.3.1.2 DAS28-ESR**

The DAS28-ESR is a measures of disease activity in 28 joints that consists of a composite numerical score of the following variables: TJC, SJC, or ESR, and Patient's Global Assessment of Disease Activity (57).

For DAS28-ESR, the 28 joints to be examined and assessed as tender or not tender for TJC and to be examined and assessed as swollen or not swollen for SJC include 14 joints on each side of the patient's body: 2 shoulders, 2 elbows, 2 wrists, 10 metacarpophalangeal joints, 2 interphalangeal joints of the thumb, 8 proximal interphalangeal joints, and 2 knees (58).

DAS28 will be derived using the following formulas from the DAS28 website (59):

$$DAS28 = 0.56 * \sqrt{(TJC28)} + 0.28 * \sqrt{(SJC28)} + 0.014 * GH + 0.70 * \ln(ESR)$$

Where:

- TJC28 = 28 joint count for tenderness
- SJC28 = 28 joint count for swelling
- $\ln(ESR)$  = natural logarithm of ESR
- GH = the general health component of the DAS (ie, Patient's Global Assessment of Disease Activity on a scale of 1 to 10 where 10 is maximal activity).

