### 7.7.2 Visual Analog Scales

Visual analog scales will include the Patient's and Physician's Global Assessment of Disease Activity, Patient's Assessment of Arthritis Pain and injection site pain.

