## Injection Site Pain

The patient's reported perception of pain will be measured on a VAS where the slash drawn by the patient represents pain of increasing intensity. The first 2 injections will be administered by qualified personnel. The next three doses of IMP (3-5) will be self-administered by the patient and injection site pain will be assessed. Pain will be recorded immediately after, 15 minutes after, and 1 hour after the injections received by the patient.

Results will be expressed in millimeters measured between the left end of the scale and the crossing point of the vertical line of the tick. This procedure is applicable for all VAS scales used in the trial.

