11.2 Inferential Methods

There will be no adjustment for multiple testing because there are only two treatment arms and a single primary endpoint. All other analyses (key secondary and other secondary endpoints) are considered as supportive to the primary endpoint.

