15.2.2.5 CDAI

The CDAI is a composite index (without acute-phase reactant) for assessing disease activity. CDAI is based on the simple summation of the swollen and tender joint counts based on 28 joints along with the Patient's and Physician's Global Assessment of Disease Activity (VAS) for estimating disease activity. The CDAI ranges from 0 to 76.

The CDAI is calculated based on the following formula:

$$CDAI = SJC28 + TJC28 + GH + PGA$$

where:

- TJC28 = 28 joint count for tenderness
- SJC28 = 28 joint count for swelling
- GH = the general health component of the DAS (i.e., Patient's Global Assessment of Disease Activity assessed using a scale of 1 to 100 where 100 is maximal activity; For analyses, GH will be divided by ten and converted to a 0.5 scale, i.e. 0, 0.5, 1, 1.5 etc. where [0-0.25] = 0, [0.25-0-75] = 0.5, [0.76-1.25] = 1, etc.)
- PGA = Physician's Global Assessment of Disease Activity assessed using a scale of 1 to 100 where 100 is maximal activity. For analyses, PGA will be divided by ten and converted to a 0.5 scale, i.e. 0, 0.5, 1, 1.5 etc. where [0-0.25] = 0, [0.25-0-75] = 0.5, [0.76-1.25] = 1, etc.

Summary statistics will be presented for the actual CDAI values and change from baseline, by visit and treatment arm, at Weeks 2, 4, 8, 12, 24 and 52.

Line graphs will also be provided to display the change from baseline over time for CDAI, by treatment arm.

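### The DAS28-ESR formula applies its 0.014 weight to a patient global score divided by ten, so scores come out too low and low-disease-activity and remission rates too high or unchanged in both arms

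*SAP*

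**What the plan says.** Protocol 7.3.1.2 and SAP 15.2.2.4 give the same formula: DAS28 = 0.56·√TJC28 + 0.28·√SJC28 + 0.014·GH + 0.70·ln(ESR), where GH is the patient's global assessment of disease activity.

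The scale of GH is described in three ways:

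- **As collected.** Protocol 7.7.2 opens "Visual analog scales will include the" and then names the patient's and physician's global assessments. Under Injection Site Pain it says results are in millimetres and adds: "This procedure is applicable for all VAS scales used in the trial".
- **In the SAP formula.** GH is "assessed using a scale of 1 to 100 where 100 is maximal activity", followed by "For analyses, GH will be divided by ten and converted to a 0.5 scale".
- **In the protocol formula.** The same 0.014 weight goes with the patient's "Global Assessment of Disease Activity on a scale of 1 to 10 where 10 is maximal activity".

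The same divide-by-ten definition of GH stands in SAP 15.2.2.5 (CDAI) and 15.2.2.6 (SDAI). Neither document changes the DAS28 weight to 0.14 or puts GH back on 0–100 for DAS28. SAP 15.2.2.4 then applies the cut-offs < 3.2 (low disease activity) and < 2.6 (remission), and SAP Section 9 lists no change from the protocol.

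**The concern.** A regression-type weight has meaning only together with the unit of its variable. DAS28-ESR is a named method, and its 0.014 belongs to a GH on 0–100. With GH divided by ten and the weight left alone, the result is no longer that score, yet it would be reported under that name and against its standard cut-offs.

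At stake are three secondary endpoints at Weeks 2, 4, 8, 12, 24 and 52: change from baseline in DAS28-ESR, the proportion with low disease activity, and the proportion in remission. The baseline DAS28 summary (SAP 12.4) and the DAS28 displays by ADA status and titer (SAP 15.3.2.1) use the same score.

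**Working it through.** **Inputs.** Weights, cut-offs and the 1.2-point significant change: SAP 15.2.2.4. Measurement error: 1.2 is described there as twice that error, so it is 0.6. Collection in mm: Protocol 7.7.2. The 0–100 mm line combines the mm rule with the SAP's upper end of 100.

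**1. Where a 0–10 global fits.** The only stated figure that depends on the scale of GH is "The CDAI ranges from 0 to 76" (SAP 15.2.2.5). With both globals on 0–10, the maximum is 28 + 28 + 10 + 10 = 76, which reproduces it. On 0–100 it would be 28 + 28 + 100 + 100 = 256. Division by ten is therefore right for CDAI.

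**2. What it does to DAS28.** Maximum contributions:

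| Term | Maximum |
|---|---|
| Tender joints | 0.56·√28 = 2.96 |
| Swollen joints | 0.28·√28 = 1.48 |
| GH in mm | 0.014·100 = 1.40 |
| GH as planned | 0.014·10 = 0.14 |

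In mm, GH is comparable with the swollen joint term. As planned, its whole range is worth 0.14/1.2 = 12% of a significant change and less than a quarter of the measurement error (0.14/0.6 = 23%).

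**3. Shortfall per score.** 0.014·GH − 0.014·(GH/10) = 0.0126·GH. Rounding to 0.5 steps moves the divided score by at most 0.25, which is 0.014·0.25 = 0.0035 points. Evaluated from 0 to 100 mm in steps of 0.01 mm, with either rounding convention at the interval edges, the shortfall is zero only at 0 mm and positive everywhere else.

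| GH (mm) | Shortfall | Correct scores wrongly below 3.2 | Correct scores wrongly below 2.6 |
|---|---|---|---|
| 30 | 0.378 | 3.20 to 3.58 | 2.60 to 2.98 |
| 40 | 0.504 | 3.20 to 3.70 | 2.60 to 3.10 |
| 60 | 0.756 | 3.20 to 3.96 | 2.60 to 3.36 |

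At 100 mm the shortfall is 1.26, more than the 1.2 called significant.

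**4. Two constructed patients.**

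- TJC28 = 2, SJC28 = 1, ESR = 18, GH = 40 mm. Without GH: 0.56·√2 + 0.28 + 0.70·ln 18 = 3.095. With GH in mm: 3.095 + 0.560 = 3.655. As planned: 3.095 + 0.056 = 3.151, counted as low disease activity.
- TJC28 = 1, SJC28 = 0, ESR = 14, GH = 30 mm. Without GH: 0.56 + 0.70·ln 14 = 2.407. With GH in mm: 2.407 + 0.420 = 2.827. As planned: 2.407 + 0.042 = 2.449, counted as remission.

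**5. Change from baseline.** If GH falls from 65 to 30 mm, it should contribute 0.014·35 = 0.49 (41% of 1.2). As planned it contributes 0.014·(6.5 − 3.0) = 0.049 (4%).

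**The case against.** - **The documents never state which scale belongs to 0.014.** They cite a website for the formula, and protocol and SAP broadly agree on a GH of about 0–10. This stands as a caveat: the premise is the definition of the named method, and the documents do not print it. It does not stand alone, though. The scale is collected in mm, a 0–10 GH makes one of four stated components almost irrelevant, and the identical definition fits CDAI's stated range.
- **The consequence is limited.** The primary endpoint is AESI incidence and the key secondary is ACR20; neither uses DAS28. SAP 11.2 says the secondary analyses "are considered as supportive to the primary endpoint". No DAS28 test or margin exists, and the rule is the same in both arms. The patient global also appears elsewhere: "Summary statistics will be presented for the actual values for the ACR component variables" (SAP 15.2.2.3), and CDAI and SDAI carry it at full weight. All of this is correct and limits the scope. It does not make the absolute DAS28 rates and changes right.
- **The direction for low disease activity needs nested categories.** If tables showed 2.6 to < 3.2 separately from < 2.6, patients pushed into remission would leave the first category, and its rate could fall. The SAP's plain < 3.2 includes remission, so the direction holds as written. The remission claim does not depend on this.
- **The practical size is unknown.** The two patients were built near the cut-offs, and the documents give no distribution of GH. No effect on rates is therefore stated.

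**Conclusion.** The concern holds. As written, the planned score is lower than DAS28-ESR by about 0.0126 × GH in mm (within ± 0.0035), and equal to it only at 0 mm. On the literal 1–100 scale every score is too low. Low-disease-activity rates (all scores < 3.2) and remission rates can only be overstated or unchanged in both arms, and the GH part of the mean change is cut to about a tenth.

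This rests on two assumptions: that 0.014 is the weight for GH on 0–100, and that the visual analog line is 100 mm long. No bias toward either arm or toward similarity is claimed. The definition should be corrected before these endpoints are produced.

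**What to change.** In SAP 15.2.2.4 and Protocol 7.3.1.2, define GH for DAS28 as the patient's global assessment VAS in mm (0–100), entered without division by ten and without rounding to 0.5. An equivalent choice is a weight of 0.14 with an unrounded 0–10 GH. Keep the divide-by-ten rule for CDAI and SDAI only. If the protocol is not amended, record the change in SAP Section 9.

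The cost is one definition line in each document (or the Section 9 entry in place of a protocol amendment) and one derivation in the analysis dataset. No new data are needed.
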